2.2. Secondary outcomes and endpoints

To determine the rate of voice and swallowing problems, patients will receive videofluoroscopic swallowing studies and voice evaluations pre-operatively and post-operatively (at Day 12, Week 6, Month 6, and 1 Year visits) to examine how voice and swallow function are affected by inclusion of a CND. Voice and/or swallow evaluations may be eliminated once necessary endpoints have been satisfied or the evaluation is no longer informative.¹

- Phonation Threshold Pressure (cm H₂O)
- Dysphonia Severity Index (DSI; +5 to -5)
- GRBAS (grade roughness breathiness asthenia strain)
- CAPE-V (0-100 on visual analog scale for voice quality parameters)
- Stroboscopy assessment (ratings 1 [most severe] to 4 [normal]) for vocal fold vibratory and movement parameters
- Glottal Function Index score
- Penetration-Aspiration Scale (0-8 score) from videofluoroscopic swallow study¹

To determine the degree to which quality of life (QOL) is compromised, qualitative analyses of patient interview data and validated surveys of general health quality, as well as QOL surveys specific to cancer, thyroid disease, voice and swallowing will be used to assess the impact of complications on patient's lives.

- SF-12 MCS and PCS scores
- EORTC QLQ C30 scale scores
- ThyCA-QOL score
- EAT-10 dysphagia inventory score
- VHI score (collected by UW ENT department during the participant's voice evaluation, and by study personnel if no voice evaluation is needed)
- Themes, codes from interview transcripts (using qualitative research methods)

¹ With the elimination of swallow studies for patients enrolled after 12/01/2016 collection of data for this endpoint ceased.

To determine whether accurate quality of life measures can be extracted from patient interview narratives, patient interview data will be converted into usable datasets using natural language processing techniques and is then compared to QoL surveys specific to cancer and thyroid disease.

- Interview transcripts
- SF-12 MCS and PCS scores
- EORTC QLQ30 scale scores
- ThyCA-QoL score

To determine clinical recurrence rates, measures of thyroglobulin levels (a reliable surrogate marker for future recurrence), and clinical evidence of recurrent disease (using either I-131 imaging or neck ultrasound), will be made at Month 6 and 1 Year visits.

- Percent of patients with a 1 Year recombinant thyroid-stimulating hormone (rTSH) stimulated Thyroglobulin level <1 ng/ml
- Unstimulated Thyroglobulin just prior to beginning the Week 6 radioactive iodine treatment
- Stimulated Thyroglobulin at the time of Week 6 radioactive iodine treatment (if RAI is given)
- Unstimulated Thyroglobulin at Month 6 >1 ng/mL
- Stimulated Thyroglobulin at 1 Year >2 ng/mL
- Biopsy-proven disease identified on neck ultrasound or I-131 uptake at either Month 6 or 1 Year post surgery, and reevaluated annually while enrolled in the study

For those patients who do experience thyroid cancer recurrence, this typically does not manifest until 10 to 20 years after their initial treatment. For this reason, in order to capture true clinical recurrence rates, participants who receive a diagnosis of PTC, as confirmed by final surgical pathology, and continue to receive care within the University of Wisconsin Hospital system will be followed through chart review in Health Link as well as University of Wisconsin's endocrine surgery outcomes database until their cancer recurs or they are lost to follow up.

Radioactive iodine treatment, ultrasound, and thyroglobulin monitoring are all part of the standard treatment and follow up of thyroid cancer for nodules >1cm. The only test that will be done for research purposes is to check the thyroglobulin level prior to radioactive iodine, so that we can assess the completeness of surgical excision prior to administering radioactive iodine.

3. Study design

This study will compare total thyroidectomy which is the standard of care treatment for PTC at the University of Wisconsin with total thyroidectomy with prophylactic CND to also remove the lymph nodes near the thyroid. Both surgical procedures are widely practiced in the United States for the treatment of thyroid cancer and it is not known which procedure is best.

Participant Identification and Eligibility:

Participants will be primarily identified from all of our University of Wisconsin endocrine surgery and otolaryngology clinics.

Eligible patients will have a thyroid nodule >1 cm in size that is consistent with or suspicious for PTC on a pre-operative biopsy. All biopsies will be reviewed by pathology to confirm eligibility. Patients with T4 (tumor of any size that extends beyond the thyroid) tumors, history of degenerative neurological diseases, pre-operative vocal cord paralysis or other vocal cord pathology will be excluded. All patients will undergo a comprehensive neck ultrasound to evaluate for lymphadenopathy by an experienced thyroid radiologist. A comprehensive evaluation of lymph nodes in levels 1-6 will be performed. If the patient is proven to have lymph node involvement they will be ineligible for the randomization arms.

Patients without evidence of nodal involvement on pre-operative imaging will be eligible for the randomization arms of the trial and consented pre-operatively. Per standard of care at our institution and the recommendations of the ATA, thyroid cancer patients are offered various surgical treatments depending on the nature of their disease. For example, for those whose cancer is limited to only one side of the thyroid, a partial lobectomy may be the appropriate treatment. For this reason, we will only approach patients who have elected to undergo total thyroidectomy for the randomization arms. Patients who are eligible for the trial but not for randomization (i.e. have evidence of lymph node disease or are choosing a thyroid lobectomy) will be approached for consent into the standard of care arm.

Pre-Operative Screening and Testing: Pre-operative laboratory testing will include calcium, PTH, and Vitamin D testing (Aim 1), a comprehensive voice and swallow¹ evaluation (Aim 2), and a complete quality of life evaluation using validated questionnaires and semi-structured interviews (Aim 3). Patients eligible for the randomization arms will then be randomly assigned - after intraoperative confirmation of no suspicious adenopathy or gross local invasion - to one of two treatments on the day of surgery; Arm 1: total thyroidectomy alone, or Arm 2: total thyroidectomy with ipsilateral prophylactic CND. Randomization will be stratified by both age and tumor size to allow appropriate comparisons between groups. Allocation schedule will not be known to study staff prior to consenting.

Operative Procedure: Total thyroidectomy will be performed using standard techniques in all patients potentially eligible for randomization. An open technique will be used to remove the entire thyroid including pyramidal lobe and all visible thyroid tissue. Care will be taken to visualize and preserve both recurrent laryngeal nerves and to preserve all parathyroids in situ. All removed specimens will be carefully examined for any parathyroid tissue and any devascularized or resected normal parathyroid glands will be confirmed by frozen section and autotransplanted into the sternocleidomastoid muscle.

For randomization patients who do not have a pre-operative diagnosis confirming PTC, a frozen section of the suspicious nodule(s) will be performed intra-operatively. If frozen section confirms PTC, the surgical procedure will continue and the patient will be randomized. If frozen section does not confirm cancer, randomization will not occur, and the operative procedure will continue according to clinical indication. During surgery, unexpected and suspicious lymphadenopathy will be biopsied. If lymph node metastases are found, then a CND would be performed at the discretion of the treating surgeon, and the patient will not be randomized. If lymph node metastases are not found in the biopsy, and the surgeon would not otherwise perform a CND based on the observed suspicious lymph node, the participant will be randomized per protocol. Once a patient has met both pre-operative intra-operative inclusion criteria and the randomization envelope is opened, he or she is enrolled in the study. Patients who screen fail intraoperatively will continue their participation with the study as part of the standard of care arm.

Patients randomized to Arm 2 will be receive total thyroidectomy with an ipsilateral CND. The CND will be performed as described by a consensus conference of the ATA. This will include removal of the prelaryngeal nodes, the pretracheal nodes, and the paratracheal lymph nodes. The paratracheal dissection will be bounded superiorly by the cricoid cartilage and inferiorly by the innominate artery on the right and on the left by the axial plane where the innominate crosses the trachea. The superior parathyroid gland will be preserved in situ along with its primary blood supply from the superior branch of the inferior thyroid artery. The inferior parathyroid gland will be reflected laterally along with its blood supply from the inferior thyroid artery. Parathyroid autotransplantation will be performed if the glands are devascularized during dissection. Paratracheal tissue specimens will be examined for parathyroid glands that may be salvaged and transplanted before being removed from the sterile field. Suspected parathyroid glands will be confirmed by frozen section biopsy prior to autotransplantation.

Blinding: Both surgical procedures are performed through the same incision and post-operative care is identical. As such, the neck dressings are identical, allowing both the patients and study staff to be masked with regard to treatment arm randomization. Participants will remain blinded to treatment arm until the Day 12 follow-up appointment, at which point their pathology report will be reviewed with them, and unblinding will occur. Because subjective symptoms and calcium intake are two of our secondary endpoints, we will minimize participant and researcher bias in the description and treatment of post-operative symptoms in the immediate post-operative period. Because the risks of the two procedures and the post-operative instructions are identical for both arms, there is no risk associated with blinding the patients until their Day 12 follow-up. Participants who screen fail intra-operatively will be notified as to which procedure(s) was conducted immediately following surgery. The surgeon performing the procedure cannot and will not be blinded to the participant's treatment arm at any time.

Post-operative follow-up: Post-operative follow-up will be done in the hospital on post-operative Day 1, and clinic follow up will occur at Day 12, Week 6, Month 6, and 1 Year. Patients will be discharged with thyroid hormone that will be administered at 1.5-1.7 mcg/kg daily. Patients will be provided a hypocalcemia symptom log and will be requested to record their calcium intake and symptoms daily. When they have symptoms they will be asked to record the time of the symptoms, what the symptoms were, the severity of the symptoms (scale of 1-5), the amount of calcium taken to treat the symptoms, and the time to symptom resolution.

All patients will be seen in follow up in the clinic in approximately 2 weeks. A calcium and PTH level will be obtained at that visit. Patients will be asked about their calcium intake and their symptoms of hypocalcemia, and their symptom log will be reviewed by study staff (Aim 1). Their symptom log will be collected at the two-week appointment and abstracted by study staff to determine the total volume of calcium supplementation consumed, the type and frequency of hypocalcemia symptoms, and the severity of those symptoms when they occurred.

Comprehensive voice and swallow⁵ evaluations will also be performed at the Day 12 visit, and these evaluations will be repeated at Week 6, Month 6, and 1 Year visits (Aim 2) if abnormalities or complaints were noted at the previous time point. All of the voice assessments listed in section 2.2 are part of a standard voice evaluation which is done routinely for patients with a history of previous neck surgery or any voice concerns, either pre-operatively or post-operatively. The video swallow exam is normally only done if there are concerns with voice or swallow function post-operatively. If deficits are observed at Day 12, appropriate treatment will be provided. This may include watchful waiting, behavioral therapy, diet modification, use of injectables, or further surgery. Follow-up assessments at Week 6, Month 6, and 1 Year will, in these cases, provide preliminary data on treatment outcomes. Patients will also complete QOL surveys and interviews to determine the effects (if any) of post-operative complications on overall well-being at each visit (Aim 3).

It is difficult to coordinate voice and swallow evaluations with regularly scheduled patient visits. If the study team is unable to schedule these procedures on the same day, the subject is given the option of returning on a different day of his or her choosing or waiving the evaluation(s) in question at that time point. If an exam is missed, the exam will be scheduled at the subject's next time point. To adequately address the secondary endpoints of the study, the study staff only needs to know if the vocal cord is working and, if it is not working, if it recovers; this can be assessed with only one post-operative time point. Ideally, the study team also hopes to understand the time course of recovery after surgery; therefore, we aim to evaluate patients at each time point. The research-only voice and swallow evaluations do not affect clinical care for thyroid cancer patients.

Subjects will receive an unstimulated thyroglobulin test approximately 6 weeks after surgery. Thyroglobulin reaches its nadir 3-4 weeks post-operatively in most patients, making the Week 6 time point ideal for collection. In multivariate analysis, the postoperative thyroglobulin level is often found to be an independent predictor of persistent or recurrent disease with a level above 0.2 ng/mL considered "elevated". Based on this result as well as the pathology report, the subject's treating endocrinologist will determine his or her risk status. According to the 2015 American Thyroid Association Management Guidelines for Adult Patients with Thyroid Nodules and Differentiated Thyroid Cancer, RAI remnant ablation is not routinely recommended after thyroidectomy in low-risk patients, although consideration of specific features of the individual patient that could modulate recurrence risk, disease follow-up implications, and patient preference are relevant to decision making regarding RAI. We will not require low-risk patients to undergo RAI remnant ablation in accordance with these guidelines; instead, their low risk status and thyroglobulin level < 0.2 ng/mL will classify their response to therapy as excellent. Should low-risk patients choose to undergo RAI remnant ablation, they will follow the protocol outlined below.

In all intermediate- and high-risk subjects and low-risk subjects who choose to undergo RAI remnant ablation therapy, radioactive iodine will be administered at 4-20 weeks post-operatively and will be administered with rTSH. For consistency all subjects will be treated with 50 mCi of radioactive iodine unless it is strongly recommended otherwise based on specific features of the individual patient. Microscopic nodal involvement found on pathologic review will not influence the treatment dose of radioactive iodine, but the presence or absence of micrometastatic versus macrometastatic disease will be tracked for future analyses. Thyroglobulin levels will be checked after the rTSH stimulation in order to assess the burden of disease prior to radioactive iodine treatment. Following radioactive iodine administration, levothyroxine will be administered to maintain TSH < 0.5 uIU/mL. Labs will be checked at 6-8 week intervals until TSH level is in the goal range and stable.

At Month 6 and 1 Year visits, TSH, unstimulated thyroglobulin and anti-thyroglobulin antibody will be measured. Additionally, all patients will receive a neck ultrasound at these time points to further evaluate for recurrence.

If the subject underwent RAI remnant ablation, recombinant TSH will be administered and a blood sample testing for the stimulated thyroglobulin level will be obtained at the 1 Year visit. If the stimulated thyroglobulin is greater than 2 ng/mL and the neck ultrasound is negative, a whole body scan will be obtained. Elevated thyroglobulin and/or positive whole body scanning will prompt further evaluation with ultrasound, CT, MRI, or CT-PET as needed. All participants will be followed for a minimum of 1 year after treatment. Long term follow-up tracking the incidence of disease recurrence will be conducted throughout the entirety of the study, with the goal of tracking patients beyond the active study phase through our prospective endocrine surgical database.

Long-term follow-up: Participants who receive a diagnosis of PTC, as confirmed by final surgical pathology, and continue to receive care within the University of Wisconsin Hospital system will be followed through chart review and the endocrine surgery outcomes database until their cancers recur or they are lost to follow up. Clinical documentation of cancer recurrence only, if it occurs, will be abstracted from their electronic medical records.

At each time point (pre-operatively, post-operative, 6 weeks after surgery, 6 months after surgery, and 1 year after surgery), a semi-structured qualitative interview will be conducted by a trained interviewer who is not a member of the clinical staff. Interview guides were developed in consultation with clinical

staff and piloted prior to use; guides include both prompted and unprompted open-ended questions aimed at understanding patient experience with various components of thyroid cancer treatment and subsequent care. All interviews will be transcribed verbatim and any identifiers will be removed from transcripts prior to coding. Data will be coded using a catalogue of focused codes developed through analysis of emergent themes in a representative subset of interview transcripts. Qualitative Health Research Consultants (QHRC), a NIH approved subcontract consisting of [name], [name], and their employees, will assist with data collection and analysis associated with qualitative aims.

Patients will also be contacted after their one year study time point to complete an electronic questionnaire about their study participation for the purposes of quality improvement, to better understand patient's perceptions of their participation in a clinical trial, and to give patients the opportunity to receive updates on study-related research in the future.

Additionally, we would like to use the coded transcripts from the interviews to customize Natural Language Processing (NLP) tools; Doing this will provide a usable training dataset from coded quality of life (QOL) surveys that the patients completed on the day of each interview. We will train NLP algorithms to turn patient narratives (transcribed interview text) into quality of life measures. That is, we aim to predict how a person would fill out a given quality of life survey tool based on their interview text. The following describes the development process:

1. The interview recordings will be transcribed by trained transcriptionists employed through the Wisconsin Surgical Outcomes Research Program (WiSOR) or an outside contractor with a business associate agreement that has been approved by UW Legal Services/Privacy Officer for HIPAA compliance. Transcriptionists have been instructed to remove identifying information from the transcripts. The audio recordings and transcripts will be shared through a secure server that only the transcriptionists and study team members have access to.
2. The completed interview transcripts will be stored on the secure network within the Wisconsin Surgical Outcomes Research Program (WiSOR). The main levels of security for this data application server housed at the SMPH Computer Center include: being securely located behind the UW-Madison campus firewall; having data directory access controls; having physical server security; and having virtual server security. The participants' names and identifying information will be stored separately from the interview transcripts. The only link between the transcripts and the identifying information will be a subject identification number contained in both data files.
3. The transcripts will be reviewed and patient narratives pertinent to quality of life will be extracted.
4. Natural language processing (NLP) tools will be used to parse the patient narratives and extract quality of life measures. A variety of parsing and machine learning strategies will be employed to maximize accuracy. Collaborators in the Department of Journalism and Mass Communications will assist with the development of these tools. All resulting data files will be stored on secure and encrypted servers.
5. The accuracy of the NLP tools will be evaluated by comparing computer generated quality of life responses to the actual patient responses and collected QOL surveys
6. The NLP tools will be customized as needed to make extraction as accurate as possible. Again, a variety of software packages and/or machine learning programming will be employed.

4. Study population

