Currently, complete removal of the thyroid (total thyroidectomy) is the primary treatment for papillary thyroid cancer (PTC). A prophylactic (preventative) central neck dissection to remove the lymph nodes near the thyroid is also often performed along with the total thyroidectomy.

A therapeutic central neck dissection (CND) is performed if there is evidence of lymph node involvement on pre-operative ultrasound or on intra-operative inspection. The removal of clearly involved lymph nodes is believed to provide a therapeutic benefit and to aid in local control of disease.

A prophylactic CND is somewhat different because it involves removing lymph nodes that are empirically *normal* on imaging and inspection with the belief that they may contain nascent disease, and if removed, will decrease the risk of recurrence. It is well established that central neck lymph nodes harbor microscopic lymph node involvement in 60% of cases. However, it has never been shown in a prospective study that prophylactic CND decreases recurrence or improves survival.

The role of prophylactic CND is one of the biggest clinical questions in the management of thyroid cancer today. With over 280 retrospective studies and reviews trying to address this question, there is still no consensus as to whether or not this procedure offers any real benefits. Instead, this procedure may place the patient at risk for serious and pervasive deficits in communicative function, nutrition, hydration, and health related quality of life (HR-QOL). Hypoparathyroidism can also result and may lead to life-threatening hypocalcemia that requires medications four or more times a day. These complications can be devastating, especially for young patients who will have to accommodate these consequences for the rest of their lives. However, removal of lymph nodes by means of a prophylactic CND at the initial operation may decrease the need for repeat surgery and its associated higher risks.

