8.2. Analysis of endpoints

For all primary aims, data will be analyzed using a mixed model two-way analysis of variance examining the effects of treatment group, time and factor interactions, such as radioactive iodine dose. Evaluation time periods (pre-surgery, Day 12, Week 6, Month 6, and 1 Year) will serve as between subjects factor and treatment group (prophylactic CND versus no CND) will serve as the between subjects factor. Experiment-wise error will be controlled with an appropriate adjustment to the alpha-level. Prior to each analysis, we will plot all data and carefully examine each analysis to ascertain that the assumptions of ANOVA are not violated. Data will be transformed as necessary to better conform to the assumptions. Nonparametric statistics will be used when assumptions for ANOVA are not achieved. Statistical support for the study design and analysis will be performed by [name] who will perform analyses with SAS statistical software (SAS Institute Inc., Cary, NC).

9. Risks and benefits of trial participation

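### Radioactive iodine use is decided after unblinding and can differ by arm, so iodine dose should not be a factor in the between-arm models of section 8.2

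*Combined protocol and SAP*

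**What the plan says.** Section 3 (Blinding) sets the time of unblinding: "Participants will remain blinded to treatment arm until the Day 12 follow-up appointment, at which point their pathology report will be reviewed with them". Section 3 (Post-operative follow-up) then describes the Week 6 unstimulated thyroglobulin and continues: "Based on this result as well as the pathology report, the subject's treating endocrinologist will determine his or her risk status". Treatment follows from that status: "In all intermediate- and high-risk subjects and low-risk subjects who choose to undergo RAI remnant ablation therapy, radioactive iodine will be administered at 4-20 weeks". Section 7 (Week 6 visit) repeats this order.

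Central nodes are removed by plan only in Arm 2 (sections 3, 5.1 and 5.2). In other patients only unexpected, suspicious nodes are biopsied, before randomisation. Section 1.1 states that "central neck lymph nodes harbor microscopic lymph node involvement in 60% of cases".

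The one safeguard is in section 3: "Microscopic nodal involvement found on pathologic review will not influence the treatment dose of radioactive iodine".

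The disease outcomes in section 2.2 include "Unstimulated Thyroglobulin at Month 6 >1 ng/mL" and biopsy-proven disease at Month 6 or 1 Year. Section 2.2 also lists a thyroglobulin taken before iodine, "so that we can assess the completeness of surgical excision prior to administering radioactive iodine". Section 8.2 proposes a mixed-model analysis of variance of "treatment group, time and factor interactions, such as radioactive iodine dose".

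**The concern.** The pathology report carries different information in the two arms. A patient with microscopic central-node disease can have it reported in Arm 2, whereas in Arm 1 the nodes stay in place and are not examined. That report feeds the risk class, and it is reviewed with a patient who, if low risk, may choose iodine. No masking of the treating endocrinologist is described. The safeguard covers how much iodine is given, not whether it is given.

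Two things follow. First, a Month 6 or 1-Year difference between arms reflects node removal plus any difference in iodine use. Second, iodine dose is a consequence of randomisation, not a baseline characteristic. Putting it in the model compares patients who are alike in iodine treatment but may no longer be alike in underlying disease, and the protection of randomisation is lost. Whether CND reduces recurrence is half of the equipoise argued in section 1.2, so a model that can distort that comparison matters.

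**Working it through.** The plan gives no figure for iodine use. Its one powered figure, 116 patients for 12% versus 36% transient hypoparathyroidism, is reproduced to within two patients (57 per arm, 114 in total; two-sided 0.05, power 0.80, continuity correction). It concerns Day 1 and does not bear on this point.

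**Order of events.** Surgery and randomisation; unblinding with pathology review at Day 12; Week 6 thyroglobulin; risk status; iodine at 4 to 20 weeks; Month 6 and 1-Year disease outcomes. The Day 1 parathyroid hormone and the Week 6 thyroglobulin come before iodine; the later disease outcomes come after it.

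**What the dose variable measures.** Section 3 fixes 50 mCi for nearly all treated subjects. Across all randomised patients, dose therefore mainly separates treated from untreated.

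**Inputs for an illustration.** From the documents: occult nodes 60% (section 1.1) and 35 to 70 patients per arm (half of 70 to 140, section 8.1). Assumed: 30% iodine use without nodal information; a share u = 25% to 75% of node-positive patients, otherwise untreated, who receive iodine because of the nodal finding; and a Month 6 event rate (thyroglobulin >1 ng/mL) of 20% without iodine and 10% with it.

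**Iodine use in Arm 2** = 0.30 + 0.70 × 0.60 × u.
- u = 0.25: 0.30 + 0.105 = 40.5%, a gap of 10.5 points.
- u = 0.75: 0.30 + 0.315 = 61.5%, a gap of 31.5 points.
- With underlying use r of 20% to 60% and u of 10% to 100%, the gap 0.60 × u × (1 − r) runs from 2.4 points (0.60 × 0.10 × 0.40) to 48 points (0.60 × 1.00 × 0.80).

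**Month 6 events with no direct CND effect.**
- Arm 1: 0.30 × 10% + 0.70 × 20% = 17.0%.
- Arm 2: 0.405 × 10% + 0.595 × 20% = 15.95%, or 0.615 × 10% + 0.385 × 20% = 13.85%.
- Differences: 1.05 and 3.15 points. The standard error, √[p₁(1−p₁)/n + p₂(1−p₂)/n], is about 8.6 to 8.9 points at 35 per arm and 6.1 to 6.3 at 70. The chance of two-sided p < 0.05 is about 5.2% to 8.1%, against a nominal 5%.

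**The direction can reverse.** Suppose CND lowers thyroglobulin, so that use apart from nodal findings is 20% in Arm 2 against 30% in Arm 1, and u = 0.10 (assumptions). Arm 2 use is then 0.20 + 0.80 × 0.60 × 0.10 = 24.8%, which is 5.2 points below Arm 1.

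**What conditioning on iodine does.** Return to 30% underlying use, and assume it is unrelated to occult nodes. In Arm 1, 60% of both treated and untreated patients had occult nodes at surgery. In Arm 2:
- Untreated: 0.60 × 0.70 × (1−u) ÷ [0.60 × 0.70 × (1−u) + 0.40 × 0.70]. This is 0.315/0.595 = 53% at u = 0.25 and 0.105/0.385 = 27% at u = 0.75.
- Treated: 0.60 × (0.30 + 0.70u) ÷ [0.60 × (0.30 + 0.70u) + 0.40 × 0.30]. This is 0.285/0.405 = 70% and 0.495/0.615 = 80%.

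Within each iodine level the arms now differ in underlying disease, although randomisation had balanced them.

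**The case against.** Several counter-arguments stand. No passage says that microscopic nodes move a patient out of low risk, and a footnote in section 7 says no patient will have significant nodal involvement. That footnote concerns dose, so it does not close the gap, but the size of any iodine difference cannot be derived. Thyroglobulin is the other input. Footnote 2 of the Schedule of activities makes a level above 2 ng/mL a reason to evaluate for iodine, while section 3 calls a level above 0.2 ng/mL elevated; those passages must be reconciled. Disease left behind in Arm 1 could raise iodine use there.

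A reader might infer that extra iodine will make CND look better than it is. The documents do not support a direction. A reader might also infer that the randomised comparison is invalid. It is not: analysis by randomised arm validly estimates the whole strategy, which may be what the optimal surgical management sought in section 1.1 means. Nor does section 2.2 present the disease outcomes as the effect of CND alone; it says only that recurrence rates will be determined.

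On section 8.2, the sentence is limited to primary aims and speaks of factor interactions, while section 2.2 places recurrence among the secondary outcomes. This weakens the point but does not remove it: sections 8.1 and 12.7 both call a recurrence endpoint primary, 8.2 is the only section on endpoint analysis, and no other rule for iodine is given.

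**Conclusion.** The point holds in a limited form. Iodine receipt can be affected by arm, and the dose safeguard does not prevent that. Month 6 and 1-Year disease results therefore describe CND plus the iodine decisions that follow, and iodine dose does not belong in the between-arm models. The 1.1 to 3.2 points are illustrative: only the 60% comes from the documents, the sign is open, and the shift is small beside a standard error of 6 to 9 points. The case for change rests on the model term rather than on a demonstrated distortion. The Day 1 primary measure is unaffected.

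It would go too far to make the Week 6 thyroglobulin the single lead disease measure. It is the cleanest view of completeness of excision, but it does not measure recurrence, which section 2.2 says typically appears after 10 to 20 years.

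**What to change.** - **Section 8.2:** delete iodine dose and its interactions from the between-arm models, and state that patients are analysed by randomised arm.
- **Reporting:** show iodine receipt by arm beside the Month 6 and 1-Year disease results, and interpret those results as effects of the strategy. Section 7.1 already collects iodine data in randomised patients.
- **Section 2.2:** reword the bullet that ties unstimulated thyroglobulin to the start of Week 6 iodine treatment. The Week 6 pre-iodine value should be compared between arms in all randomised patients, as the measure of completeness of excision that iodine cannot affect. It is added to the recurrence outcomes and replaces none of them.

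The cost is wording in two sections and one descriptive table. The blood test is already scheduled, and no change to iodine treatment is proposed. The small downside is a narrower interpretation of the later disease results.
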